5.3 Concomitant and Excluded Medications

- If a subject is taking any medication, the medicine, dose and duration must be recorded on the Concomitant Medication Form.
- Excluded medications are indicated in the Subject Exclusion criteria; the use of any excluded medications during the study may result in discontinuation of the subject, pending review with the study physician, investigator and sponsor to determine the impact of the medicine and duration of use on acne.

5.4 SUBJECT RESPONSIBILITIES

The subject responsibilities are as follows:

- Subjects must not use any other light based devices
- Subjects may not receive professional or aesthetic facial spa procedures during the course of the study.
- Subjects may follow their normal bathing routine
- Subjects must not shave or use other hair removal methods on their faces within 24 hours of visits
- Subjects must be willing and able to follow all study directions, including avoiding excessive sun exposure (including tanning beds), which could lead to a change in the visible appearance of skin such as sunburn or tanning effect, and to commit to all follow up visits for the duration of the study.
- Subjects must be willing to cleanse their face and remove ALL facial and ALL eye makeup at least 30 minutes (and maximum of 2 hours) prior to every study visit. If an individual wears makeup to their visit, they will remove it in the clinic with a Sponsor-provided non-medicated cleanser and undergo a waiting period of at least 15 minutes prior to having grading performed.

5.5 CONCURRENT PRODUCTS

- Subjects may continue using their regular brand(s) of non-medicated facial products such as moisturizers, eye makeup removers, color cosmetics, and sunscreens within the following specifications:
 - must have been used for at least one month prior to study start
 - must be non-medicated and do not contain benzoyl peroxide, salicylic acid, alpha hydroxy acids (AHAs), vitamins A (retinol) or C (ascorbic acid) or their analogs or derivatives.

Protocol Title: A SINGLE-CENTER CLINICAL STUDY TO EVALUATE THE TOLERANCE OF AN ACNE TREATMENT IN SENSITIVE SKIN SUBJECTS WITH MILD TO MODERATE ACNE VULGARIS

Protocol identification: CO-1701-2511-3728-SACT

Date: 9 March 2017 Final Version 1.0

- must not have exfoliating properties (cleansers with exfoliating beads, scrubs, masks)
- Subjects must not introduce new product or change products during the course of the study
- **Site staff will record the products that the subject is currently using at baseline [paper capture only].**

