4 STUDY DURATION

This study will take place over a 28-day period, with the subjects presenting to the test center for 3 visits. Visits will be at Screening/Baseline (Day 0/Visit 1), Day 14 (Visit 2) and Day 28 (Visit 3).

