5.2.1 Inclusion Criteria

1. Subjects must read, sign, and receive a copy of the IRB-approved informed consent /assent as applicable.
2. Females and males.
3. Age: 12 to 40 years old.
4. Subjects with Fitzpatrick Skin Types of I – VI
5. Individuals who are generally in good health as determined by the investigator and study physician, based on medical history reported by the subject.
6. Acne criteria - Subjects must have a mild to moderate acne vulgaris on the face, as defined by an Investigator's Global Assessment Score of 2 or 3 using the Modified Cook's Scale as defined in section 8.2.
7. Sensitive Skin Criteria - Subjects must successfully meet the Sensitive Skin Criteria according to Sensitive Skin Inclusion Criteria questionnaire as defined in section 8.2.
8. Cutaneous Tolerance scores of 0 or 1 (no greater) in all tolerance parameters
9. Subjects must have used current consistent facial products for at least 1 month prior to study start.
10. Individuals who are able to read, speak, write, and understand English.
11. Females determined to be of child-bearing potential must agree to take a pregnancy test to confirm that they are not pregnant, and females must indicate they are not lactating nor do they intend to become pregnant during their participation in the study (subject must document their response in either the source documentation or informed consent form).

Male and Female subjects with reproductive potential must agree to practice a medically acceptable form of birth control during the study (through Week 4) or for 30 days following the last dose of investigational product whichever is later. Females must have used such birth control for at least 3 months prior to the Baseline visit.

Medically acceptable forms of birth control that may be used by the subject and/or his/her partner include:

- Established use of hormonal methods of contraception (oral, injected, implanted, patch or vaginal ring) for a minimum of 90 days prior to baseline

Protocol Title: A SINGLE-CENTER CLINICAL STUDY TO EVALUATE THE TOLERANCE OF AN ACNE TREATMENT IN SENSITIVE SKIN SUBJECTS WITH MILD TO MODERATE ACNE VULGARIS

Protocol identification: CO-1701-2511-3728-SACT

Date: 9 March 2017 Final Version 1.0

- Barrier methods of contraception with spermicide: condom or occlusive cap (diaphragm or cervical/vault caps) with spermicidal foam/gel/film/cream/suppository.
- Intrauterine device (IUD) or intrauterine system (IUS)

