5.2.2 Exclusion Criteria

Subjects with any of the hereafter criteria must be excluded from the study:

1. Has a known light or photo-sensitivity disorder.
2. Subjects with very sensitive skin, atopic dermatitis, and/or known allergies or sensitivities to ingredients contained in the cleanser (i.e. fragrance, preservatives, etc.), and/or other known medical conditions that in the opinion of the Investigator would cause them to be excluded.
3. Subjects with severe acne or acne conglobata.
4. Subjects who have pre-existing, dormant or active facial dermatologic conditions (e.g., psoriasis, rosacea, atopic dermatitis, rashes, many and/or severe excoriations, etc.) that could interfere with the outcome of the study as determined by the Investigator.
5. Female who (to the best of her knowledge) is pregnant, lactating, or planning to become pregnant during the study or within 30 days of study completion
6. Male whose female partner is (to the best of his/her knowledge) pregnant or planning to become pregnant during the study or within 30 days of study completion.
7. Subjects who report that they have used topical tretinoin (Retin-A®, Retin-A Micro®, Renova®, Adapalene, Tazarotene), Avita®, Tazorac®, Avage®, Differin®, Azelaic acid, benzoyl peroxide, Dapsone, Sodium sulfacetamide, or Epiduo or other similar prescription drug, and/or other prescription medications for acne such as Doxycycline, Minocycline, Clindamycin, Bactrim, Tetracycline, Erythromycin, and Vibramycin within 2-weeks of the study start,

Protocol Title: A SINGLE-CENTER CLINICAL STUDY TO EVALUATE THE TOLERANCE OF AN ACNE TREATMENT IN SENSITIVE SKIN SUBJECTS WITH MILD TO MODERATE ACNE VULGARIS

Protocol identification: CO-1701-2511-3728-SACT

Date: 9 March 2017 Final Version 1.0

8. Subjects who have taken Accutane or other oral retinoid within the past 6 months.
9. Subjects who report starting a new prescription medication (oral or topical) that can make skin more sensitive, cause photosensitivity, or have an effect on the skin (i.e. antibiotics, hormones (not including those used for contraception), insulin, inhaled steroids (with the exception of inhaled steroids prescribed for allergies) etc.) within 1 month prior to entry. Subjects may continue on a regular course of medication that they have been using for more than 1 month, and for which they will continue using routinely for the full course of the study, if they are stable in the opinion of the Investigator or designee.

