10. Subjects using OTC topical medications on the face (excluding sunscreens, which are allowed) and/or soaps/makeup that contain topical medications (including anti-acne or antibacterial agents, topical anti-inflammatories, topical retinoids, salicylic acid etc.) within a 2-week period before the start of the study.
11. Individuals who have observable suntan, scars, nevi, tattoo, excessive hair, etc. or other dermal conditions on the face that might influence the test results in the opinion of the Investigator or designee
12. Subjects concurrently participating in any other clinical study (i.e., dermal patch, use tests, investigational drug or devices, etc.), or having participated in another facial clinical study within 30 days from the start of the study.
13. Subjects viewed by the Investigator as not being able to complete the study.
14. An individual who has any condition which in the PI's judgment makes the candidate inappropriate for study participation.
15. Individuals with a history of immunosuppression/immune deficiency disorders (including HIV infection or AIDS) or currently using immunosuppressive medications (e.g., azathioprine, belimumab, cyclophosphamide, Enbrel, Imuran, Humira, mycophenolate mofetil, methotrexate, prednisone, Remicade, Stelara.), and/or radiation as determined by study documentation.
16. Individuals with an uncontrolled disease such as asthma, diabetes, hypertension, hyperthyroidism, or hypothyroidism. Individuals having multiple health conditions may be excluded from participation even if the conditions are controlled by diet, medication, etc.
17. Individuals with any planned surgeries and/or invasive medical procedures during the course of the study.

Protocol Title: A SINGLE-CENTER CLINICAL STUDY TO EVALUATE THE TOLERANCE OF AN ACNE TREATMENT IN SENSITIVE SKIN SUBJECTS WITH MILD TO MODERATE ACNE VULGARIS

Protocol identification: CO-1701-2511-3728-SACT

Date: 9 March 2017 Final Version 1.0

18. Subjects who are related to those persons involved directly or indirectly with the conduct of this study (i.e., PI, sub-investigators, study coordinators, other site personnel, employees of Johnson & Johnson subsidiaries, contractors of Johnson & Johnson, and the families of each

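### Section 5.5 bars AHA, vitamin C and exfoliating products on study, but no visible entry criterion requires subjects to be off them before the Day 0 baseline

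*Combined protocol and SAP*

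**What the plan says.** **On-study limits (Section 5.5).** Subjects may keep their regular facial products, but these "must be non-medicated and do not contain benzoyl peroxide, salicylic acid, alpha hydroxy acids (AHAs), vitamins A (retinol) or C (ascorbic acid", analogs and derivatives included. They also "must not have exfoliating properties (cleansers with exfoliating beads, scrubs, masks". A further rule reads: "Subjects must not introduce new product or change products during the course of the study". Baseline products are recorded, on paper only.

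**Entry criteria (Sections 5.2.1 and 5.2.2).** Inclusion 9 reads: "Subjects must have used current consistent facial products for at least 1 month prior to study start". Exclusion 10 applies to "Subjects using OTC topical medications on the face (excluding sunscreens, which are allowed) and/or soaps/makeup that contain topical medications", and continues: "including anti-acne or antibacterial agents, topical anti-inflammatories, topical retinoids, salicylic acid etc.) within a 2-week period before the start of the study". Exclusion 7, also with a two-week window, begins "Subjects who report that they have used topical tretinoin (Retin-A®, Retin-A Micro®, Renova®, Adapalene, Tazarotene" and goes on to other acne drugs, including benzoyl peroxide. Inclusion 8 admits baseline tolerance scores of 0 or 1.

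**Timing (Sections 4, 7.5 and 8).** "Visits will be at Screening/Baseline (Day 0/Visit 1), Day 14 (Visit 2) and Day 28 (Visit 3". Tolerance scoring and the first supervised use of the regimen both take place at Visit 1.

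**Design and analysis (Sections 7.2.1 and 9).** The study is open label with one arm. Section 9 tests the mean change from baseline against zero, two-sided at 0.05, and reports the percent mean change and the percent of subjects improved or worsened. It also summarises and tabulates the scores by visit and lists adverse events.

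**The concern.** The products barred during the study and the products excluded before it are not the same set. Where they differ, the baseline score can be taken on one background routine and the Day 14 and Day 28 scores on another, with the switch made on the day the test regimen starts.

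A controlled trial would have this switch in both arms. Here there is no comparator, so a change caused by dropping a background product looks the same as a change caused by the mask and cleanser. If the dropped product was irritating the skin, its fading irritation counts as improvement and can offset new irritation in the mean. In a tolerance study that is the error one most wants to avoid.

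**Working it through.** **Step 1: compare the two lists.**

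| Class barred by 5.5 | Covered by a two-week entry window? |
|---|---|
| Benzoyl peroxide | Yes: Exclusion 7, and as an anti-acne agent under Exclusion 10 |
| Salicylic acid | Yes: named in Exclusion 10 |
| Vitamin A and analogs | Mostly: topical retinoids in Exclusion 10, prescription retinoids in Exclusion 7. Open for cosmetic retinol not regarded as a medication |
| AHAs | Not named |
| Vitamin C and analogs | Not named |
| Exfoliating cleansers, scrubs, masks | Not named |

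Exclusion 10's list is open-ended, but it lists kinds of topical medication. A cosmetic AHA or vitamin C moisturizer, or a scrub, is not clearly one.

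**Step 2: follow one subject.** She has used an AHA moisturizer daily for several months. Inclusion 9 is met, since it limits duration and not ingredients. Exclusions 7 and 10 do not name her product. Inclusion 8 is met if she scores 0 or 1. She is scored at Visit 1 while on the product and starts the regimen at the same visit. From then on 5.5 forbids the moisturizer, and 5.5 also forbids changing products. She cannot satisfy both rules, and no criterion says whether she is to be excluded, deferred or enrolled.

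**Step 3: effect on the mean change.** The plan gives no figure to reproduce: Section 6 states only up to 45 enrolled for 40 completers. Inclusion 8 caps baseline at 1, so a resolving irritant moves one subject's score by at most -1. If a fraction f of subjects move this way, the mean change shifts by -f.

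Assumptions, none of them from the documents: 10% to 30% of 40 subjects use such a product, half of these score 1 on a given sign because of it, and all of those resolve.

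- Low: 40 × 0.10 × 0.5 = 2 subjects; shift -2/40 = -0.05
- High: 40 × 0.30 × 0.5 = 6 subjects; shift -6/40 = -0.15

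If stopping a moisturizer instead raised dryness by one point in 2 to 6 subjects, the same arithmetic gives +0.05 to +0.15.

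**Step 4: effect on the test.** The table naming the test is not shown, so a one-sample t-test with n = 40 is assumed (critical value 2.02 on 39 degrees of freedom). If k subjects fall by one point and nobody else changes, p = k/40, SD = √[(40/39) × p(1 − p)] and |t| = p / (SD/√40).

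- k = 3: p = 0.075, SD = 0.267, |t| = 1.78, not significant
- k = 4: p = 0.100, SD = 0.304, |t| = 2.08, significant improvement

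A simulation used 20,000 runs per cell. Each subject changed by -1 with probability f (withdrawn irritant resolves), by +1 with probability w (regimen irritates), and otherwise by 0.

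| f | w = 0: significant improvement | w = 10%: significant worsening | w = 20%: significant worsening |
|---|---|---|---|
| 0 | 0% | 57.2% | 97.2% |
| 5% | 13.8% | 11.5% | 47.2% |
| 10% | 57.6% | 2.2% | 19.6% |
| 15% | 87.2% | 0.4% | 6.9% |

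These figures show how sensitive the test is. They do not predict what this study would find, since f and w are both assumed.

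**Step 5: the percentages.** A resolving irritant adds to percent improved. It does not cancel another subject's rise, which still counts as worsened. Percent worsened is affected only within a subject: one who starts at 1 because of the old product and is then irritated to 1 by the regimen shows no change.

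**The case against.** The strongest reply is that the plan, read sensibly, keeps such subjects out. Section 5.5 permits continuation only within its limits and forbids changes, so a habitual user of a barred product is unsuitable. Section 8 has concurrent products reviewed alongside eligibility before scoring, Section 5.4 requires willingness to follow directions, and Exclusions 13 and 14 give the investigator discretion. A careful site might well screen her out. What stands is that no visible text requires it, so sites could differ. Equally, nothing tells the site to enroll her and stop the product that day. That sequence follows from reading the rules together and is not a stated procedure.

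Four stronger readings are tempting, and the documents do not support them.

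- **Vitamin A has no washout.** Exclusions 7 and 10 cover retinoids. Only cosmetic retinol might slip through.
- **Every tolerance result is compromised.** Section 9 also tabulates scores by visit, and new rises still count in percent worsened. Adverse events are listed separately.
- **The bias must favour the product.** Nothing in the documents shows that irritation fades by Day 14 or Day 28, and losing a moisturizer could raise dryness or tightness.
- **The bias is large.** No usage figures are given. A population that considers its facial skin sensitive most or all of the time may use few scrubs or AHAs.

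The schedule of events, the success criteria and parts of the design text are also not shown. A pre-visit instruction there cannot be ruled out.

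**Conclusion.** The mismatch is real and can be checked in the text. AHA, vitamin C and exfoliating products, and cosmetic retinol unless it is read into Exclusion 10, are barred on study with no visible requirement to be off them before Day 0. For a steady user, the two rules in 5.5 contradict each other.

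The consequence is confounding of the mean change, its test and the percent improved or worsened with withdrawal of a background product. For an irritant the likely direction is towards better apparent tolerance, but the direction is not established for every product. The size is unknown. The shift of -0.05 to -0.15 rests on assumed usage, assumed baseline scores and full resolution, and the test results rest also on an assumed t-test. If few entrants use these products, the effect is small. It should be corrected because the remedy is simple and a single-arm analysis cannot separate the two effects afterwards.

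**What to change.** Reconcile the entry criteria with Section 5.5:

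1. Apply Exclusion 10's existing pre-study window to every class that 5.5 prohibits: AHAs, vitamin A and vitamin C with their analogs or derivatives, and exfoliating cleansers, scrubs and masks.
2. In Inclusion 9, define the current consistent products as those that 5.5 permits.

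Baseline and follow-up are then scored on the same background products, and the conflict with the no-change rule disappears.

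The cost is two wording changes and some delay in recruitment. A candidate who simply stops a barred product is deferred by two weeks. One who substitutes a new product is deferred by about a month, because the substitute must meet the one-month rule in Inclusion 9 and 5.5. The amended text should state this so that sites apply it alike.

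As a supplement, the baseline product record could be entered in the database and the tolerance results summarised by baseline product use. That costs data entry for up to 45 subjects. It would show how often the problem arose but would not remove it.

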5.6 SCREENING FAILURE

All individuals who sign the ICD/Accent Document and withdraw their participation or fail to meet all of the eligibility/screening criteria during the initial evaluation will be considered a "screening failure."

Data from screen failure subjects will not be considered in the final report.

6 SAMPLE SIZE DETERMINATION

A sufficient number of subjects will be screened to enroll up to 45 subjects to complete with 40 total subjects.

Protocol Title: A SINGLE-CENTER CLINICAL STUDY TO EVALUATE THE TOLERANCE OF AN ACNE TREATMENT IN SENSITIVE SKIN SUBJECTS WITH MILD TO MODERATE ACNE VULGARIS

Protocol identification: CO-1701-2511-3728-SACT

Date: 9 March 2017 Final Version 1.0

Protocol Title: A SINGLE-CENTER CLINICAL STUDY TO EVALUATE THE TOLERANCE OF AN ACNE TREATMENT IN SENSITIVE SKIN SUBJECTS WITH MILD TO MODERATE ACNE VULGARIS

Protocol identification: CO-1701-2511-3728-SACT

Date: 9 March 2017 Final Version 1.0

7.2 RANDOMIZATION

There will be no randomization.

7.2.1 Blinding

This is an open label, single-arm study. There is no blinding.

7.3 STUDY MATERIAL STORAGE AND ACCOUNTABILITY

The PI must ensure that deliveries of investigational study materials from the Sponsor are correctly received by a responsible person and that the investigational study materials are stored in a secure area under recommended storage conditions: all test products and devices at room temperature (59° - 77°F) in a secured and locked room that is only accessible by authorized site personnel.

The PI must maintain adequate records documenting the receipt, use, loss, damage or other disposition of the investigational products and devices on the Investigational Product Accountability Log or equivalent.

The log must identify the investigational products and devices and account for their disposition on a subject by subject basis, including specific dates and quantities dispensed and returned.

The log must be signed by the individual who dispensed/retrieved the investigational products and devices and a copy must be provided to the Sponsor for the Trial Master File at end of study.

At the end of the study, after final reconciliation of all investigational products and devices is complete, the investigational products and devices must be packaged and returned to the Sponsor at the following address:

7.4 PRODUCT QUALITY COMPLAINTS

A Product Quality Complaint (PQC) is any written, electronic, or oral communication that alleges deficiencies related to the identity, quality, durability, reliability, or safety of a product, including its labeling, delivery system or packaging integrity. It also includes device malfunctions. This does not include effectiveness, preference, or performance measures. Any PQC discovered during the initial inventory should follow the instructions provided on the receipt letter; no PQC form should

Protocol Title: A SINGLE-CENTER CLINICAL STUDY TO EVALUATE THE TOLERANCE OF AN ACNE TREATMENT IN SENSITIVE SKIN SUBJECTS WITH MILD TO MODERATE ACNE VULGARIS

Protocol identification: CO-1701-2511-3728-SACT

Date: 9 March 2017 Final Version 1.0

be filed for issues identified when opening or unpacking a shipment. Subsequently, any observation of a PQC requires immediate notification to the Study Manager via a completed PQC form and telephone call. The PI or designee should complete, sign, and forward a copy of the PQC form to the Study Manager

In addition, PQC information must be included on the Investigational Product accountability and reconciliation Form or equivalent in the comments field. The Study Manager listed can assist you or answer questions related to this process. To aid in the initial conversation and understanding of a PQC, the site staff may be asked to photograph the issue and send it to the Study Manager.

When enrolling subjects into this study, it is the site's responsibility to instruct subjects not to use the investigational product if they have a concern related to the labeling, investigational product) or package integrity and to immediately report it using the instruction on the ICD or investigational product label.

7.5 USE OF THE INVESTIGATIONAL PRODUCTS AND DEVICE

Prior to use, the subject will receive education and documentation on proper use of the product and device. Subjects will acknowledge understanding of the instructions and a copy of signed acknowledgement will be sent home with them for reference. The first use of the investigational products or device will be under clinic supervision on Visit 1/Day 0.

When the products are distributed, the subjects will be given detailed instructions for use as directed in Appendix I, as well as in the inserts provided with the test products.

Subjects will also receive an IRB approved diary to track compliance.

7.5.1 INSTRUCTIONS:

Detailed subject instructions are in Appendix I.

